#### **7.6.3.1 Criteria to Resume Treatment**

Subsequent dosing with study therapy may resume once drug-related non-DLT AEs resolve to Grade 1 or baseline.

Participants experiencing AEs not meeting criteria for permanent discontinuation as outlined in [Section 8.2](#) may resume treatment with study medication under the following criteria:

- Participants may resume study treatment when the drug-related AE(s) resolve to Grade  $\leq$  1 or baseline value, with the following exceptions:
  - Participants may resume treatment in the presence of Grade 2 fatigue.

- Participants who have not experienced a Grade 3 drug-related skin AE may resume treatment in the presence of Grade 2 skin toxicity.
- Participants with Grade 2 uveitis, episcleritis, iritis, eye pain, or blurred vision not meeting DLT criteria ([Section 8.2](#)) must resolve to baseline prior to resuming study therapy.
- For participants with Grade 2 AST, ALT, or total bilirubin elevations, dosing may resume when laboratory values return to baseline and management with corticosteroids (if needed) is complete.
- Participants with combined Grade 2 AST/ALT **and** total bilirubin values meeting DLT criteria ([Section 7.6.1](#)) should have treatment permanently discontinued.
- Drug-related pulmonary toxicity, diarrhea, or colitis must have resolved to baseline before treatment is resumed. Participants with persistent Grade 1 pneumonitis after completion of a steroid taper over at least 1 month may be eligible for re-treatment if discussed with, and approved by, the BMS Medical Monitor (or designee).
- Participants with drug-related endocrinopathies adequately controlled with only physiologic hormone replacement may resume treatment.
- Participants with confirmed SARS-CoV-2 infection may resume treatment after 1) at least 10 days (20 days for severe/critical illness) have passed since symptoms first appeared, positive RT-PRC test result, or positive viral antigen test result, 2) resolution of acute symptoms (including at least 24 hours has passed since last fever without fever reducing medications), 3) evaluation by the investigator with confirmation that there are no sequelae that would place the participant at a higher risk of receiving investigational treatment, and 4) consultation by the medical monitor. For suspected cases, treatment may also resume if SARS-CoV-2 infection is ruled-out and other criteria to resume treatment are met.
  - Prior to re-initiating on-study treatment in a participant with a dosing delay lasting 8 weeks due to SARS-CoV-2 infection, the medical monitor/designee must be consulted.

#### **7.6.4      *Exceptions to Permanent Discontinuation Criteria***

Any drug-related AE occurring at any time that meets DLT criteria as outlined in Section 7.6.1 will require permanent discontinuation, **with the exception of the following:**

- Grade 3, nausea, vomiting, or abdominal pain that returns to Grade 1 or baseline within or at 48 hours either spontaneously or with medical intervention.
- Grade 3 pruritus or rash that returns to Grade 1 or baseline within 7 days with medical intervention.
- Isolated Grade 3 or 4 electrolyte imbalances/abnormalities that are not associated with clinical sequelae and are corrected with supplementation/appropriate management within 3 days of their onset.
- Grade 4 neutropenia < 7 days in duration.
- Grade 4 lymphopenia or leukopenia.
- Grade 3 increase in amylase or lipase that is not associated with clinical or radiographic evidence of pancreatitis.
- Grade 3 infusion reactions that return to Grade 1 in < 6 hours.

- Grade 3 fever not associated with hemodynamic compromise (eg, hypotension, clinical, or laboratory evidence of impaired end-organ perfusion).
- Grade 3 tumor flare (defined as pain, irritation, or rash that localizes to sites of known or suspected tumor).
- Grade 3 fatigue.
- Grade 3 or 4 drug-related endocrinopathy AEs, such as adrenal insufficiency, adrenocorticotropic hormone, hyper- or hypothyroidism, or glucose intolerance, which resolve or are adequately controlled with physiologic hormone replacement (corticosteroids, thyroid hormones) or glucose-controlling agents, respectively, may not require discontinuation after discussion with and approval from the BMS Medical Monitor (or designee).
- Any event that leads to delay in dosing, lasting > 8 weeks from the previous dose, requires discontinuation, with the exception of the following:
  - Dosing delays for prolonged steroid tapers to manage drug-related AEs are allowed. Prior to re-initiating treatment in a participant with a dosing delay lasting > 8 weeks from the previous dose, the BMS Medical Monitor (or designee) must be consulted. Tumor assessments should continue as per protocol even if dosing is delayed. Periodic study visits to assess safety and laboratory studies should also continue Q4W, or more frequently if clinically indicated, during such dosing delays.
  - Dosing delays lasting > 8 weeks from the previous dose that occur for non-drug-related reasons may not require discontinuation, if approved by the BMS Medical Monitor (or designee). Prior to re-initiating treatment in a participant with a dosing delay lasting > 8 weeks, the BMS Medical Monitor (or designee) must be consulted.
- Any AE, laboratory abnormality, or concurrent illness, which, in the judgment of the Investigator, presents a substantial clinical risk to the participant with continued nivolumab dosing.

Even if the criteria to resume treatment are met, the consideration to re-initiate study therapy under the following exception will be made on a case-by-case basis after considering the overall benefit-risk profile and in consultation between the Investigator and the Sponsor. Any AE with clinical risk will be assessed on a case-by-case basis with the Investigator and the BMS Medical Monitor (or designee), to determine the risks and benefits of continuing on therapy following resolution vs discontinuing therapy permanently.

All participants who discontinue IP should comply with protocol specified follow-up procedures as outlined in [Section 2](#) and [Section 8.2](#). The only exception to this requirement is when a participant withdraws consent for all study procedures including post treatment study follow-up or loses the ability to consent freely (eg, imprisonment, involuntarily incarceration for the treatment of either a psychiatric or physical illness).

If study treatment is discontinued prior to the participant's completion of the study, the reason for the discontinuation must be documented in the participant's medical records and entered on the appropriate case report form (CRF) page.

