### **7.6.1 Dose-limiting Toxicities**

For the purpose of guiding dose escalation, DLTs will be defined based on the incidence, intensity, and duration of AEs that are possibly related to study treatment. The DLT period will be 8 weeks (56 days) in both the BMS-986218 Monotherapy Dose Escalation (Part 1A) and the Safety Evaluation of Combination Doses of BMS-986218 with Nivolumab (Part 1B). Any toxicities that occur beyond the DLT period will be accounted for in making final dose level decisions.

Participants receiving 2 doses of BMS-986218 and have completed or who discontinued due to a DLT in the 8-week DLT period will be considered as DLT-evaluable participants for BMS-986218 monotherapy. Participants receiving either 2 doses each of BMS-986218 and nivolumab, or participants who discontinued due to a DLT in the 8-week combination treatment DLT period, will be considered as DLT-evaluable participants for combination treatment. Participants who withdraw from the study during the DLT evaluation period or have received less than 2 doses for reasons other than a DLT in both monotherapy and combination therapy will not be considered as DLT-evaluable participants and may be replaced with a new participant at the same dose level. Participants who have received 2 doses and withdraw from the study during the last week of the DLT evaluation period for reasons other than a DLT in both monotherapy and combination therapy may be considered as DLT-evaluable. Participants who are dose delayed during the DLT evaluation period for reasons other than a DLT in both monotherapy and combination therapy could be considered as DLT-evaluable participants if they received 2 doses and completed at least 2 full cycles of therapy 4 weeks each, with a maximum of 12 weeks for the total duration, including delays.

For the purpose of participant management, any AE that meets DLT criteria, regardless of the cycle in which it occurs, will lead to discontinuation of study treatment. Participants who withdraw from the study during the 8-week DLT evaluation period for reasons other than a DLT may be replaced with a new participant at the same dose level. The incidence of DLT(s) during the 8-week DLT evaluation period will be used in dose escalation decisions and to define the MTD. AEs occurring after the DLT period will be considered for the purposes of defining the RP2D upon agreement between the Sponsor, Medical Monitor (or designee), and Investigators.

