Participants experiencing a DLT will not be re-treated with study treatment and will enter the Safety Follow-up Period of the study. DLTs occurring after the 8-week DLT observation period will be accounted for in determining the dose levels for expansion.

AEs will be graded according to the NCI CTCAE v4.03.

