### **7.6.1.5 Other Dose-limiting Toxicities**

Any of the following events will be considered a DLT:

- Grade 2 drug-related uveitis, episcleritis, iritis eye pain, or blurred vision that does not respond to topical therapy and does not improve to Grade 1 severity within the re-treatment period OR requires systemic treatment.
- Grade 3 drug-related uveitis, episcleritis, iritis, pneumonitis, bronchospasm, or neurologic toxicity.
- Grade  $\geq 4$  hypersensitivity reaction or Grade 3 that does not resolve to Grade 1 in  $< 6$  hours.
- Other  $\geq$  Grade 3 study treatment-related toxicity will be considered a DLT. However, the following Grade 3 or 4 events will **not** be considered DLTs:
  - Grade 3 or Grade 4 electrolyte abnormalities that are not complicated by associated clinical adverse experiences, last less than 48 hours, and either resolve spontaneously or respond to conventional medical intervention. Confirmatory laboratory test is required within 48 hours.
  - Grade 3 nausea or vomiting that lasts less than 48 hours, and either resolves spontaneously or responds to conventional medical intervention.
  - Grade 3 or Grade 4 elevation of amylase or lipase not associated with clinical or radiographic evidence of pancreatitis.
  - Grade 3 fever not associated with hemodynamic compromise (eg, hypotension, clinical or laboratory evidence of impaired end-organ perfusion).
  - Grade 3 endocrinopathy that is well controlled by hormone replacement.
  - Grade 3 tumor flare (defined as pain, irritation, or rash that localizes to sites of known or suspected tumor).
  - Grade 3 fatigue.
  - Grade 3 infusion reaction that returns to Grade 1 in  $< 6$  hours.

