# **8 DISCONTINUATION CRITERIA**

## **8.1 Discontinuation from Study Treatment**

Participants MUST discontinue for any of the following reasons:

- Documented disease progression as defined by RECIST v1.1 ([Appendix 5](#)) or per PCWG 3 criteria for prostate ([Appendix 12](#)) unless participants meet criteria for treatment beyond progression ([Section 8.1.1](#)).
- Clinical deterioration while receiving active study therapy that, in the opinion of the Investigator, indicates that continued participation in the study is not in the best interest of the participant.
- Any drug-related AE occurring at any time that meets DLT criteria as outlined in [Section 7.6.1](#) will require permanent discontinuation. Exceptions to permanent discontinuation are listed in [Section 7.6.4](#).
- Participant's request to stop study treatment. Participants who request to discontinue study treatment will remain in the study and must continue to be followed for protocol-specified follow-up procedures. The only exception to this is when a participant specifically withdraws consent for any further contact with him/her or persons previously authorized by participant to provide this information.
- Any clinical AE, laboratory abnormality or intercurrent illness that, in the opinion of the Investigator, indicates that continued participation in the study is not in the best interest of the participant.
- Termination of the study by BMS.
- Loss of ability to freely provide consent through imprisonment or involuntarily incarceration for treatment of either a psychiatric or physical (eg, infectious disease) illness. (Note: Under specific circumstances, and only in countries where local regulations permit, a participant who has been imprisoned may be permitted to continue as a participant. Strict conditions apply and BMS approval is required.)
- Inability to comply with protocol.
- Discretion of the Investigator.
- Pregnancy.

- Individual participants with confirmed CR will be given the option to discontinue study therapy on a case-by-case basis after specific consultation and agreement between the Investigator and BMS Medical Monitor (or designee) in settings where benefit-risk justifies discontinuation of study therapy.
- Any event that leads to delay in dosing lasting > 8 weeks from the previous dose requires discontinuation, with the following exceptions:
  - Dosing delays for prolonged steroid tapers to manage drug-related AEs are allowed.

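### Section 7.6.4 places two stopping rules among the exceptions to stopping, and exempts dose-limiting toxicities after which Section 7.6.1 says treatment must end

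*Combined protocol and SAP*

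**What the plan says.** Four places in the protocol govern stopping after a DLT.

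- **Section 7.6.1** gives a rule for managing participants: "any AE that meets DLT criteria, regardless of the cycle in which it occurs, will lead to discontinuation of study treatment". It adds: "Participants experiencing a DLT will not be re-treated with study treatment and will enter the Safety Follow-up Period of the study". Neither sentence mentions exceptions or refers to Section 7.6.4.
- **Section 7.6.1.5** ends with a catch-all that makes other treatment-related toxicity of Grade 3 or higher a DLT, followed by a list of events that are not DLTs. One of these is "Grade 3 or Grade 4 electrolyte abnormalities that are not complicated by associated clinical adverse experiences, last less than 48 hours", provided they resolve or respond to treatment.
- **Section 7.6.4** opens with "Any drug-related AE occurring at any time that meets DLT criteria as outlined in Section 7.6.1 will require permanent discontinuation" and then introduces a bulleted list of exceptions. The list includes isolated electrolyte abnormalities that "are corrected with supplementation/appropriate management within 3 days of their onset", and "Grade 4 lymphopenia or leukopenia". Its last two bullets are of another kind: delays beyond 8 weeks, which the bullet itself says call for discontinuation, and any event that in the Investigator's judgement "presents a substantial clinical risk to the participant with continued nivolumab dosing".
- **Section 8.1** is the mandatory discontinuation list. It includes "Any clinical AE, laboratory abnormality or intercurrent illness that, in the opinion of the Investigator, indicates that continued participation" is against the participant's interest. It repeats the DLT rule with a pointer to the Section 7.6.4 exceptions, and it carries the 8-week delay rule with its two exceptions.

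**The concern.** An exceptions list should contain only events after which treatment may go on. This one also holds two rules whose evident purpose is to stop treatment, so their literal effect is reversed. In addition, Section 7.6.1 states the general rule as absolute, so two sites that follow different sections to the letter can treat the same event in opposite ways.

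These passages decide whether a participant is dosed again with a first-in-human antibody after a dose-limiting event. Adverse events leading to discontinuation are also part of the primary safety endpoint (Tables 1-1 and 4-1), and Part 2A sets safety beside ipilimumab. If stopping practice differs between sites because the text differs between sections, that count partly reflects the wording.

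**Working it through.** The check compares passages; the only arithmetic is a count of places and one conversion of units.

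**1. The substantial-risk bullet.** Under the Section 7.6.4 stem, every bullet is a case where permanent discontinuation is not required. The last bullet is an event that the Investigator already considers a substantial risk if dosing continues. Section 8.1 lists investigator-judged events under a stem that says participants must discontinue. The two give opposite instructions for closely parallel events.

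**2. The drug named.** The bullet refers to nivolumab alone. From the maxima in Section 5.2:
- no nivolumab: Part 1A 200 + Part 2A 160 + Part 2B 120 = 480
- nivolumab: Part 1B 84 + Part 2C 80 + Part 2D 40 = 204
- total: 480 + 204 = 684, which matches the protocol's figure

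So 480 of 684 planned places (70%) are in parts where the bullet's wording refers to a drug that is not given.

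**3. The 8-week rule.** It is worded as a stopping rule, stands in the exceptions list, and is already in Section 8.1.

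**4. Events that are DLTs but exempt.** Three days is 3 × 24 = 72 hours.

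| Event | Not a DLT under 7.6.1.5 if | Exempt from stopping under 7.6.4 if | DLT, yet exempt |
|---|---|---|---|
| Uncomplicated Grade 3-4 electrolyte abnormality | under 48 h | corrected within 72 h | 48 to 72 h |
| Endocrinopathy controlled by replacement | Grade 3 | Grade 3 or 4, after Medical Monitor approval | Grade 4 |
| Grade 3 abdominal pain | not carved out | back to Grade 1 or baseline by 48 h | resolving by 48 h |

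Abdominal pain counts as a DLT because the catch-all reaches gastrointestinal events outside the gastrointestinal section: nausea and vomiting had to be carved out of it. In each row Section 7.6.1 ends treatment and bars re-treatment, while Section 7.6.4 allows continuation. Grade 3 nausea or vomiting resolving at exactly 48 hours is a further boundary case.

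**5. Bullets without conflict.** Grade 3 fatigue, fever without hemodynamic compromise, tumor flare, amylase or lipase elevation without pancreatitis, and infusion reactions returning to Grade 1 in under 6 hours are already not DLTs. Exempting them changes nothing.

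**6. Lymphopenia and leukopenia.** Section 7.6.1.3 does not name them, so their status depends on the catch-all. If it covers hematologic events, they are DLTs from Grade 3 upward. But then uncomplicated Grade 3 thrombocytopenia would also be a DLT, and the bleeding-or-transfusion condition in Section 7.6.1.3 would do no work. If it does not cover them, they are not DLTs at any grade and need no exception. Their presence in Section 7.6.4 does not decide it, because step 5 shows that the list includes non-DLTs. The text is ambiguous. Grade 3 pruritus raises the same question for skin events and is not counted here.

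**The case against.** The strongest reply is that this is a rule with exceptions working as intended. Section 7.6.4 restates the DLT rule and qualifies it, and Section 8.1, the operative discontinuation section, points to those exceptions. An exceptions list must exempt something the rule covers, so a 72-hour limit beside a 48-hour limit is not in itself an error. That last part stands: differing thresholds alone are not the fault. What remains is that Section 7.6.1 states its rule for participant management, not only for dose escalation, and makes it absolute with no pointer onward.

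It can also be said that nobody would read the substantial-risk bullet as permission to dose. Section 7.6.3 withholds treatment for potential DLTs, Section 8.1 allows stopping at the Investigator's discretion, and the paragraph after the bullet calls for case-by-case review with the Medical Monitor. These safeguards are real and make harm from the bullet less likely. They do not remove the contradiction, since Section 8.1 sends the reader back to the list that contains it. Navigation is also unreliable: Sections 7.6.3 and 7.6.3.1 send sites to Section 8.2 for permanent-discontinuation criteria, but that section concerns leaving the study.

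A reader might infer that Grade 3 lymphopenia ends treatment while Grade 4 does not. The documents do not support this as a finding, because it requires the catch-all to cover hematologic events, and step 6 shows that this is unsettled.

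**Conclusion.** Wrong as written, on two counts. Two stopping rules sit among the exceptions to stopping, one of them in conflict with Section 8.1 and limited to a drug that Parts 1A, 2A and 2B do not use. Section 7.6.1 also forbids continuation that Section 7.6.4, with Section 8.1 pointing to it, permits for at least three kinds of DLT. A third matter, whether lymphopenia and leukopenia are DLTs, is ambiguous.

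The text applies in every part, but its effect cannot be sized. The figure of 684 is the ceiling on evaluable participants, not the number affected, and no frequency is given for any of these events. A reader might infer a measurable bias in the comparison with ipilimumab. The documents do not support that: the safety analyses are descriptive, no hypothesis is formally tested (Section 3.2.1), and nothing shows how sites apply the text. The case for correcting it rests on participant safety and on a consistent meaning for a primary safety endpoint component. The conclusion assumes only that sites may follow any of these sections as written.

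**What to change.** In the next amendment, reconcile Sections 7.6.1, 7.6.1.5, 7.6.4 and 8.1 so that one instruction applies to each event:

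1. Take the substantial-risk bullet and the 8-week delay rule out of the Section 7.6.4 exceptions and rely on Section 8.1, which already has the delay rule and an investigator-judgement rule covering all study treatments.
2. If any of the substantial-risk wording is kept, make the drugs it names match what each arm receives.
3. Make the two Section 7.6.1 sentences and the Section 7.6.4 exceptions agree, in whichever direction the sponsor intends.
4. State whether the catch-all in Section 7.6.1.5 covers hematologic events.
5. Correct the references to Section 8.2 in Sections 7.6.3 and 7.6.3.1.

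This does not require a single duration or grade across sections; thresholds are for the sponsor's medical team. The cost is wording only, with no new procedure, visit or participant.

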### **7.6.5 Management of Drug-related Infusion Reactions**

Since BMS-986218, ipilimumab, and nivolumab contain only human Ig protein sequences, they are unlikely to induce hypersensitivity reactions. However, based on the non-clinical toxicology evaluation of BMS-986218, infusion reactions due to T-cell activation and cytokine release may occur in both monotherapy and combination with nivolumab. If such a reaction were to occur, it might manifest with fever, chills, rigors, headache, rash, pruritus, arthralgia, hypotension, hypertension, bronchospasm, or other allergic-like reactions. All Grade 3 or 4 infusion reactions should be reported within 24 hours to the BMS Medical Monitor (or designee) and reported as an SAE. Infusion reactions should be graded according to NCI CTCAE v4.03 guidelines.

Treatment recommendations for infusion reactions are provided below and may be modified based on local treatment standards and guidelines, as appropriate.

For Grade 1 symptoms (mild reaction; infusion interruption not indicated; intervention not indicated):

- Remain at bedside and monitor participant until recovery from symptoms. The following prophylactic premedications are recommended for future infusions: diphenhydramine 50 mg (or equivalent) and/or acetaminophen/paracetamol 325 to 1000 mg at least 30 minutes before study treatment administrations.

For Grade 2 symptoms (moderate reaction requiring therapy or infusion interruption but responding promptly to symptomatic treatment such as antihistamines, non-steroidal anti-inflammatory drugs, narcotics, corticosteroids, bronchodilators, IV fluids, or prophylactic medications indicated for  $\leq 24$  hours):

- Stop the study treatment infusion, begin an IV infusion of normal saline, and treat the participant with diphenhydramine 50 mg IV (or equivalent) and/or acetaminophen/paracetamol 325 to 1000 mg; remain at bedside and monitor participant until resolution of symptoms. Corticosteroid and/or bronchodilator therapy may also be administered as appropriate. If the infusion is interrupted, then restart the infusion at 50% of the original infusion rate when symptoms resolve; if no further complications ensue after 30 minutes, the rate may be increased to 100% of the original infusion rate. Monitor participant closely. If symptoms recur, then no further BMS-986218, ipilimumab, or nivolumab will be administered at that visit.
- For future infusions, the following prophylactic premedications are recommended: diphenhydramine 50 mg (or equivalent) and/or acetaminophen/paracetamol 325 to 1000 mg should be administered at least 30 minutes before study treatment infusions. If necessary, corticosteroids (up to 25 mg of hydrocortisone or equivalent) may be used.

For Grade 3 or 4 symptoms (severe reaction, Grade 3: prolonged [ie, not rapidly responsive to symptomatic medication and/or brief interruption of infusion]; recurrence of symptoms following initial improvement; hospitalization indicated for other clinical sequelae [eg, renal

impairment, pulmonary infiltrates]; Grade 4: life-threatening; pressor or ventilatory support indicated):

- Immediately discontinue infusion of study treatment. Begin an IV infusion of normal saline and treat the participant as follows: recommend bronchodilators, epinephrine 0.2 to 1 mg of a 1:1000 solution for subcutaneous administration or 0.1 to 0.25 mg of a 1:10,000 solution injected slowly for IV administration, and/or diphenhydramine 50 mg IV with methylprednisolone 100 mg IV (or equivalent), as needed. Participant should be monitored until the Investigator is comfortable that the symptoms will not recur. Study treatment will be permanently discontinued except for a Grade 3 infusion reaction that returns to Grade 1 in less than 6 hours. Investigators should follow their institutional guidelines for the treatment of anaphylaxis. Remain at bedside and monitor participant until recovery of the symptoms.

In the case of late-occurring hypersensitivity symptoms (eg, appearance of a localized or generalized pruritus within 1 week after treatment), symptomatic treatment may be given (eg, oral antihistamine or corticosteroids).

